Our division has recently described the feasibility and utility of the use NIV using a RAM Nasal Cannula (NIV/RAM-NC) in the outpatient setting [1]. NIV/RAM-NC inpatient initiation has become more common as more data are available about the use of this new technology. Standardized protocols of how NIV/RAM-NC should be implemented and monitored are lacking here at both the inpatient and outpatient site in Children’s Memorial Hermann Hospital.

Rationale:

NIV/RAM-NC has the potential to improve transition from invasive ventilation to NIV. In the process of weaning and depending on the underlying pulmonary pathophysiologic disorder, patients may require positive pressure for long-term management in order to be discharged from hospital. At this time, the availability of NIV interfaces that can be used in the outpatient setting are limited to BIPAP and CPAP with nasal or full-face mask. These approaches restrict the use of positive pressure delivery devices in the pediatric setting due

to several factors, including: patient age, weight, mask fitness, tolerability of the interface, facial developmental and skin irritation and breakdowns [7-8]. We propose the implementation of a standardized protocol to initiate NIV/RAM-NC with Trilogy mechanical ventilator at the Children Memorial Hospital inpatient and outpatient site.

Objectives:

Primary Aims:

- Implement a standardized protocol to initiate NIV/RAM-NC with Trilogy mechanical ventilator at the Children Memorial Hospital inpatient and outpatient site.

Secondary Aims:

- Explore the side effects and complications associated with the use of NIV/RAM-NC in children.

Study Design and Methods

Overview: A one-year prospective study will be conducted in order to enroll subjects to start NIV/RAM-NC. Demographic data, clinical diagnosis, NIV RAM Cannula mode and parameters, associated complications, side effects and mortality information will be collected from the electronic medical record at the end of the year. Descriptive statistics will be obtained and presented in percentage and averages.

Study Population:

Children from 0 to 21 years admitted to the Children Memorial Hermann Hospital and consulted to Pediatric Pulmonary Service for initiation of NIV/RAM-NC both at the inpatient and outpatient.

Inclusion Criteria:

Children who fail to wean from chronic respiratory support (CPAP, BiPAP, HFNC) in whom long-term ventilation is considered between 10/2016 – 10/2017 will be included.

Exclusion Criteria:

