Children with minimal setting (CPAP < 5cmH₂O, HFNC < 3LPM) able to be weaned to

regular nasal cannula and patients with upper airway obstruction that may be candidates for surgical procedure will be excluded.

Study Procedures:

Patient Risks: Risk related to the use of NIV/RAM-NC include:

- Ulceration and pressure necrosis due to the interface long-term use.
- Skin breakdown and ulceration of the nasal septum
- Abdominal distension due to aerophagia
- Aspiration of gastric content
- Nasal sinus congestion
- Air trapping and risk of pneumothorax (air leak)
- Need of further procedures (ex. chest tube)

Patient Benefits:

- Prevent invasive procedures like tracheostomy tube cannulation
- Avoid the use of traditional facial interfaces for positive pressure delivery and their complications
- Potential decrease the length of the total hospitalization

Study Outcomes

Our goal is to safely initiate and monitor the use of NIV/RAM-NC implementation in the inpatient and outpatient setting at Children Memorial Hospital and promote an adequate transition to home NIV ventilation with Pediatric Pulmonary follow up.

Data Analysis Plan

At the end of the study, data will be extracted from the electronic medical record (Care4) McGovern Medical School, UT Health. Statistical collaboration from UT will be used for data analysis, if needed. Data analysis will be encrypted with a password that will be known by the principal investigator and research co-workers. Percentage analysis for the epidemiology and risk factors information from the EMR will be analyzed for each variable. Graphical analysis from multiple variables for hypothesis testing will be part of the study.

Sample size and power

Based on our experience about the use of NNIV with RAM Cannula, we expect to enroll around 50 subjects to be part of the study. No power known at this time due to the limited use of NIV/RAM-NC in the pediatric population and the scant literature on this topic. Our sample will depend on the number of patients consulted to initiate NIV/RAM-NC at the inpatient and outpatient setting.

Limitations

Limited use of NIV/RAM-NC in the pediatric population may affect our enrollment and observations. We expect to implement a protocol and describe our experience with our NIV/RAM-NC children cohort.

Confidentiality

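### The plan promises graphs for hypothesis testing without naming a hypothesis, test or error rate, and names no measure of precision for complication percentages from about 50 children

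*Combined protocol and SAP*

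**What the plan says.** The combined protocol and SAP describes its analysis in several places.

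- **Data Analysis Plan:** "Graphical analysis from multiple variables for hypothesis testing will be part of the study." The sentence before it reads "Percentage analysis for the epidemiology and risk factors information from the EMR will be analyzed for each variable." The section also says "Statistical collaboration from UT will be used for data analysis, if needed."
- **Study Design and Methods, Overview:** "Descriptive statistics will be obtained and presented in percentage and averages." Complications, side effects and mortality are among the data to be taken from the medical record at the end of the year.
- **Secondary Aims:** "Explore the side effects and complications associated with the use of NIV/RAM-NC in children."
- **Sample size and power:** "we expect to enroll around 50 subjects to be part of the study", followed by "No power known at this time due to the limited use of NIV/RAM-NC in the pediatric population". The final number depends on how many children are referred.
- **Limitations:** "Limited use of NIV/RAM-NC in the pediatric population may affect our enrollment and observations." The section then says that the investigators expect to put a protocol in place and describe their own cohort.
- **Confidentiality:** age, sex and ethnicity are collected to look for differing patterns across demographic groups.
- **What will we measure?:** success is monitored through work of breathing, respiratory rate, blood gases, oximetry and chest X-ray. The first two are worded as improvement. Baseline blood gas, oximetry and chest X-ray are requested before the device is started.
- **Interpretation and Potential Importance of Findings:** the investigators expect to describe the safety of starting the device in children generally.

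**The concern.** Two linked problems follow.

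First, the Data Analysis Plan commits to hypothesis testing but does not say what is tested, how, or at what error rate. A graph does not supply a test or control an error rate. With several variables and about 50 children, some patterns will appear by chance. Under this sentence they could be reported as test results, and no rule set beforehand would let a reader judge them.

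Second, the stated output for complications is a percentage, and no interval is named. The plan intends to speak about safety in children beyond its own cohort. A percentage from about 50 children does not show how high a complication rate the data still allow. This matters most when a complication is not seen at all, because a bare zero can be read as evidence of safety.

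**Working it through.** **Step 1. Set the statements side by side.**

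| Section | What it implies |
|---|---|
| Overview | Descriptive; percentages and averages |
| Secondary Aims | Exploratory |
| Limitations; Interpretation and Potential Importance of Findings | Descriptive |
| Confidentiality | Comparison across demographic groups; no test named |
| What will we measure? | Change from baseline; no test named |
| Data Analysis Plan | Hypothesis testing by graphs; no hypothesis, test or error rate named |
| Sample size and power | Power not known |

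Comparative intent is therefore present but not specified. The size of the first problem cannot be calculated, because neither the number of comparisons nor an error rate is given.

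**Step 2. Inputs for the precision check.**

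The expected n of 50 comes from Sample size and power. It is an enrolment expectation, so there is no calculated figure in the plan to reproduce. The plan gives no expected complication rate and no confidence level. The event counts, the 95% level, and n = 30 and n = 60 are therefore assumptions. The two other sample sizes are shown because the final number depends on referrals and Limitations says enrolment may be affected.

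**Step 3. No events observed.**

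The upper end of the exact (Clopper-Pearson) two-sided 95% interval is 1 − 0.025^(1/n).

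- n = 50: 1 − 0.025^(1/50) = 7.1%
- n = 30: 1 − 0.025^(1/30) = 11.6%
- n = 60: 1 − 0.025^(1/60) = 6.0%

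**Step 4. An observed 10% at n = 50, that is 5 events.**

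With x events in n children, the lower limit is the 2.5% quantile of Beta(x, n − x + 1). The upper limit is the 97.5% quantile of Beta(x + 1, n − x).

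- Lower: 2.5% quantile of Beta(5, 46) = 3.3%
- Upper: 97.5% quantile of Beta(6, 45) = 21.8%

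As a check on method, the Wilson interval for 5/50 is 4.3% to 21.4%, so the message does not depend on the choice of interval.

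**Step 5. Chance of seeing no event at all in 50 children.**

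For an assumed true rate p this is (1 − p)^50.

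- p = 2%: 0.98^50 = 36%
- p = 1%: 0.99^50 = 61%

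An observed zero is thus quite possible for complications that do occur at these rates.

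**The case against.** The strongest reply has four parts.

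**The plan is not purely descriptive.** A reader might infer that it contains no comparison, so that the hypothesis-testing sentence is simply out of place and should be struck. The documents do not support that. The Confidentiality section looks for demographic patterns, and the list of measures implies change from baseline. This part stands: the fault is under-specification, and the documents do not show whether the investigators want a test.

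**The sentence may be only loose wording.** It could mean graphs that accompany tests left to the university statisticians. That is possible, so it cannot be said that graphs will certainly be presented as tests, only that the text allows it. Some background text is also not available, and a hypothesis could have been stated there. Even so, the Data Analysis Plan itself names no test and no error rate, and statistical help offered only if needed does not fill that gap.

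**Intervals are a reporting preference.** This is an exploratory quality improvement project, and a percentage with its denominator describes the cohort fully. Any reader could compute an interval from it. Nothing in the plan rules intervals out, so a reader who infers that they are excluded goes too far. The argument would largely succeed if the plan stayed with its own cohort. It weakens because the plan intends to describe safety in children generally and foresees a manuscript.

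**The figures show only how wide binomial intervals are at small n.** This is true. They illustrate what a bare percentage leaves out, and they do not measure harm from the hypothesis-testing sentence.

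**Conclusion.** The point holds as a minor one. The Data Analysis Plan commits to hypothesis testing through graphs while the available text leaves the hypothesis, test and error rate unstated. The plan also names no measure of precision for complication percentages from a small cohort of uncertain size.

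At the expected 50 children, no events would still be compatible with a true rate of up to 7.1%, and an observed 10% with anything from 3.3% to 21.8%. With no events, the upper limit runs from 11.6% at 30 children to 6.0% at 60. These figures rest on assumed event counts, an assumed 95% level and, apart from 50, assumed sample sizes.

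A reader might go on to infer that the study is underpowered and needs a sample-size justification. The documents do not support this: the aims are to implement and explore, the plan openly says that power is not known, and a descriptive study needs no power calculation.

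**What to change.** **1. Replace the hypothesis-testing sentence.** Two options are equally acceptable, and the investigators should choose the one that matches their intent.

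- State that the graphs, the patterns by age, sex and ethnicity, and the changes from baseline are descriptive and exploratory.
- If a test is intended, name the hypothesis, outcome, test and error rate before the records are extracted.

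**2. Add one reporting sentence.** Report each complication as n/N and percentage with an exact 95% interval for the number actually enrolled. Have any statement about safety cite the upper limit.

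The cost is one sentence replaced, one added and a few lines of code. Eligibility, treatment and data collection do not change. The downside is that the results will look less certain.
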